### **10.1.3 SAE reporting**

To ensure participant safety, every SAE, regardless of causality, occurring after the participant has provided informed consent and until 30 days after last study visit must be reported to Novartis Safety immediately, without undue delay, under no circumstances later than within 24 hours of learning of its occurrence. Detailed instructions regarding the submission process and requirements are to be found in the investigator folder provided to each site. Information about all SAEs is collected and recorded on the Serious Adverse Event Report Form; all applicable sections of the form must be completed in order to provide a clinically thorough report.

Any SAEs experienced after the 30 day period should only be reported to Novartis Safety if the investigator suspects a causal relationship to study treatment unless otherwise specified by local law/regulations. Any SAEs reported up to the participant’s last visit will be reported in the eCRF and the Novartis Safety database. SAEs beyond that date will only be recorded in the Novartis Safety database.

All follow-up information for the SAE including recurrent episodes, information on complications, progression of the initial SAE and recurrent episodes must be reported as follow-up to the original episode immediately, without undue delay, and under no circumstances later than within 24 hours of the investigator receiving the follow-up information. An SAE occurring at a different time interval or otherwise considered completely unrelated to a previously reported one must be reported separately as a new event.

If the SAE is not previously documented in the Investigator’s Brochure or Package Insert (new occurrence) and is thought to be related to the investigational treatment, a Chief Medical Office and Patient Safety (CMO&PS) Department associate may urgently require further information from the investigator for Health Authority reporting. Novartis may need to issue an Investigator

Notification (IN) to inform all investigators involved in any study with the same investigational treatment that this SAE has been reported.

Suspected Unexpected Serious Adverse Reactions (SUSARs) will be collected and reported to the competent authorities and relevant ethics committees in accordance with EU Guidance 2011/C 172/01 or as per national regulatory requirements in participating countries.

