Detailed instructions regarding the submission process and requirements are to be found in the investigator folder provided to each site.

Consider the following 3 categories (as applicable) to determine SAE reporting timeframes:

1. To ensure patient safety, every SAE, regardless of causality, occurring after the participant has provided informed consent and until 30 days after the last study visit must be reported to Novartis within 24 hours of learning of its occurrence.
2. Any SAEs experienced after the 30 days period should only be reported to Novartis if the investigator suspects a causal relationship to study treatment.
3. Recurrent episodes, complications, or progression of the initial SAE must be reported as follow-up to the original episode, regardless of when the event occurs. This report must be submitted within 24 hours of the investigator receiving the follow-up information. An SAE that is considered completely unrelated to a previously reported one should be reported separately as a new event.

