## **Adverse events**

All information obtained on AEs will be displayed by treatment group (or sequence) and participant.

Treatment emergent AEs will be summarized by actually received treatment.

Treatment emergent AEs (TEAE) are defined as:

- Events started after the first dose of study treatment (ligelizumab) in this study and within 16 weeks of last dose of study treatment
- Events present prior to the first dose of study treatment (ligelizumab) in this study but:
  1. increased in severity based on preferred term (e.g. worsening of headache),
  2. same PT but increased severity (e.g. from mild to moderate),
  3. same PT but increase in seriousness (from non-serious AE to SAE; if already a SAE from medical significant to LT/fatal)and within 16 weeks after the last dose of the study treatment.

The number (and percentage) of participants with treatment emergent AEs will be summarized in the following ways:

- by treatment, primary system organ class and preferred term.
- by treatment, primary system organ class, preferred term and maximum severity.
- by treatment, Standardized MedDRA Query (SMQ) and preferred term.

Separate summaries will be provided for study medication related AEs, death, SAEs, other significant adverse events leading to treatment discontinuation.

The number (and proportion) of participants with treatment emergent AEs of special interest (AESI) will be summarized by treatment.

The number (and proportion) of participants with treatment emergent AEs related to other safety topics such as events related to “liver toxicity” will be summarized by treatment.

A participant with multiple AEs within a primary system organ class is only counted once towards the total of the primary system organ class.

For the placebo-ligelizumab treatment group, treatment-emergent AEs will be counted separately for the placebo treatment and ligelizumab treatment.

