2.7.1 Adverse events (AEs)

Treatment emergent adverse events (TEAEs) are events which started on or after the first dose of study treatment and within 16 weeks after the last study treatment, or events present prior to the first dose of study treatment but increased in severity based on preferred term within 16 weeks after the last study treatment.

TEAEs will be summarized in each cohort separately by the actually received treatment group:

- The number and exposure-adjusted incidence of subjects having any TEAE by system organ class (SOC) and preferred term (PT): For the participants in the placebo arm, adverse events after switching to ligelizumab (on or after Week 12) will be summarized separately for the treatment phase. The summary of the TEAEs up to Week 12 will include all the TEAEs up to Week 12 for all the treatment groups, including the placebo only group. The summary of the TEAEs for the entire study will be provided for all the treatment groups listed in Table 2-3.
- The number and exposure-adjusted incidence of subjects having any TEAE by severity: if a subject reported more than one adverse event with the same preferred term, the adverse event with the greatest severity will be presented. If a subject reported more than one adverse event within the same primary system organ class, the subject will be counted only once with the greatest severity at the system organ class level, where applicable.
- The number and exposure-adjusted incidence of subjects having any related TEAEs.: if a subject reported more than one adverse event with the same preferred term, the adverse event with the greatest severity will be presented. If a subject reported more than one adverse event within the same primary system organ class, the subject will be counted only once with the greatest severity at the system organ class level, where applicable.
- The number exposure-adjusted incidence of subjects having any serious treatment emergent adverse events (TESAEs), related TESAEs. The following significant adverse event will be listed - TEAEs leading to discontinuation and dose interruption, and TEAE adverse events of special interest (AESIs). For AESIs with adjudication (anaphylaxis, malignancy, CCV), separate listings will be provided based on the adjudicated results.
- A listing will be provided for safety topics of immunogenicity, COVID-19 infection, Liver Toxicity.

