2.7.1.1 Exposure-Adjusted Incidence Rate

Due to expected differences in exposure and follow-up due to varied duration of study participation between participants, adverse event incidence rates will be provided as “exposure adjusted AE incidence rates”.

The EAIR is defined as the number of subjects with a specific event divided by the total exposure-time among the subjects in the study group. That is, the EAIR is calculated as:

$EAIR = n / \sum t_i$, where n is the number of subjects having the i^{th} type event, and t_i is a subject's exposure time and defined as the shortest of the following:

- 1) time to the first episode of the i^{th} type event (if the event occurs),
- 2) duration of study treatment plus the 16-week washout period (approximately corresponding to five half-lives) after last treatment dose, or
- 3) end of the analysis period (Week 12 for the placebo period, week 36 for all safety follow-up).

The total exposure time of all subjects in a treatment group is $\sum t_i$. The EAIR is interpreted as the number of events occurring in a population per unit time. The exact Poisson 95% confidence interval for the EAIR will be provided as well, where an exact $100*(1-\alpha)\%$ confidence interval will be derived as follows (Garwood 1936, Sahai and Khurshid 1993):

- Lower confidence limit $L = \frac{0.5C_{\alpha/2,2n}}{\sum t_i}$ for $n>0$, 0 otherwise,
- Upper confidence limit $U = \frac{0.5C_{1-\alpha/2,2n+2}}{\sum t_i}$,

where $C_{\alpha,k}$ is the α th quantile of the Chi-square distribution with k degrees of freedom.

Whenever applicable, exposure adjusted incidence rates will be provided for the type as below:

1. TEAE and TESAE: Primary SOC level, PT level
2. Most frequent (at least 5% in any treatment group) TEAE: Primary SOC level, PT level

Treatment emergent AE of special interest.

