2.7.2 Deaths

Death will be reported as part of TESAE with a fatal outcome and will be listed in separate listings.

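### For participants who leave the study less than 16 weeks after their last dose, treatment-emergent SAEs after the last visit have no stated route into the safety outputs, while their person-time is still counted in the entire-study rates

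*Protocol*

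**What the plan says.** **Where SAEs are recorded (Protocol 10.1.3).** SAEs reported up to the participant's last visit "will be reported in the eCRF and the Novartis Safety database". For later ones, "SAEs beyond that date will only be recorded in the Novartis Safety database". Sites report every SAE, whatever its cause, until 30 days after the last study visit. Beyond that, "Any SAEs experienced after the 30 days period should only be reported to Novartis if the investigator suspects a causal relationship to study treatment".

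**What counts as treatment emergent.** Protocol 12.5.2 (Adverse events) takes events that start after the first dose and "within 16 weeks of last dose of study treatment". SAP 2.7.1 agrees: "events which started on or after the first dose of study treatment and within 16 weeks after the last study treatment". Both are anchored to the last dose, not to the last visit.

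**Person-time (SAP 2.7.1.1).** Each participant contributes the shortest of three times: the time to the first event, the "duration of study treatment plus the 16-week washout period" after the last dose, or the end of the analysis period (Week 12 or Week 36).

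**Deaths (SAP 2.7.2).** "Death will be reported as part of TESAE with a fatal outcome and will be listed in separate listings".

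**Who stays in follow-up.** Protocol 9.1.1 expects participants who stop treatment to complete the follow-up visits. Protocol 9.1.2 defines leaving the study as ending both treatment and follow-up.

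**The concern.** Capture in the eCRF ends at the last visit, while treatment emergence and person-time end 16 weeks after the last dose. If the last visit comes first, the sponsor still receives all SAEs for up to 30 more days. By its own definition those inside the 16 weeks are treatment emergent, yet the protocol places them only in the safety database. Neither document describes a transfer into the analysis data. Protocol 11.2 describes eCRF and vendor data, then lock and release for analysis.

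The outputs at stake are the TESAE and AESI tables, the death listing and the registry SAE tables. The numerator can lose events while the denominator keeps the time, so the error runs towards lower rates. It falls on people who left early, for whom a health event is a plausible reason for leaving. Efficacy analysis has been dropped (SAP Section 4), so these safety outputs are the main product that remains.

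**Working it through.** **1. Calendar check.** Table 8-1 puts the last dose at Week 20 (Day 141) and the last visit at Week 36 (Day 253). 16 weeks = 112 days, and 141 + 112 = 253. This reproduces the statement in Protocol 3.1 that Week 36 is 16 weeks after the last dose. Completers have no gap.

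**2. A participant who leaves early.** Without an event, counted time is t = min(last dose + 16, 36) weeks from first dose. The documents do not give the timing of a leaver's last visit; I assume 4 weeks after the last dose.

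| Last dose | Counted time | Last visit | Without eCRF capture | Share of counted time |
|---|---|---|---|---|
| Week 0 | 16 wk | Week 4 | 12 wk | 75% |
| Week 8 | 24 wk | Week 12 | 12 wk | 50% |
| Week 20 | 36 wk | Week 24 | 12 wk | 33% |

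If the last visit falls 0 to 8 weeks after the last dose, the uncovered time is 16 to 8 weeks. Of the 12 weeks (84 days) in the table, the first 30 days have all-causality SAE reporting, to the safety database only. In the other 84 - 30 = 54 days only SAEs suspected to be related are reported.

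**3. Share of an arm's person-time.** Take an arm on ligelizumab from Day 1, drop-out fraction d, completers contributing 36 weeks and all leavers stopping at the same dose:

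share = 12d / [36(1 - d) + d t]

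- d = 10% (the planning value in Protocol Section 5): t = 16 gives 1.2/34.0 = 3.5%; t = 24 gives 1.2/34.8 = 3.4%; t = 36 gives 1.2/36.0 = 3.3%.
- d = 5%: 0.6/35 to 0.6/36 = 1.7%.
- d = 15%: 1.8/33 = 5.5% to 1.8/36 = 5.0%.

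With the event count held fixed, the rate is lower by this share than if person-time stopped at the last visit. Events missing from the numerator would lower it further.

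**4. Would transferring the SAEs be enough?** Not entirely. The 54 days remain without all-causality reporting: 54/7 = 7.7 weeks, and 0.1 × 7.7 = 0.77; 0.77/36 to 0.77/34 = 2.1% to 2.3%. The denominator rule needs its own correction.

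**5. Ceiling on follow-up that is reported but has no route to the tables.**

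- As planned: 10% of 428 = 43 people; 43 × 30/365.25 = 3.5 participant-years. Thirty days is 30/112 = 27% of the window.
- As enrolled (39, SAP 1.1): 10% is about 4 people; 4 × 30/365.25 = 0.3 participant-years.

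These are upper limits. Anyone last seen more than 112 - 30 = 82 days after the last dose has fewer than 30 window days left, and people who withdrew consent are counted in the 10%.

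**6. A related ambiguity.** SAP 2.4.1 defines exposure as last minus first dose date plus 28 days. If that is the duration meant in SAP 2.7.1.1, person-time can run to 20 weeks after the last dose (capped at Week 36) and the gap widens by up to 4 weeks.

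**The case against.** **The plan does not say that the outputs leave these SAEs out.** A reader might infer that it does. Protocol 10.1.3 says where late SAEs are recorded; the SAP defines its outputs by onset and outcome and names no source. The opening of SAP 2.1 is not in the public text I could read, and a source or lock rule could stand there. The sponsor may also reconcile the two databases routinely. This stands as a limit: exclusion is inferred from the word *only* and from the absence of a transfer step in the visible text.

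**Fatal outcomes.** A reader might infer that a death learned of after the last visit is lost even when the SAE itself is already in the eCRF. The documents do not support this: Protocol 10.1.3 treats progression as follow-up to the original SAE, and 10.1.1 follows AEs to resolution.

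**Not every table.** For participants who stop before Week 12, and for placebo participants who never switch, SAP 5.2 can end the Week 12 period at study exit or death and applies that cut-off to the AE summary tables. SAP 2.7.1.1 says Week 12. The excess person-time is therefore clear only for the entire-study tables.

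**Not everyone who stops treatment.** Protocol 9.1.1 keeps these participants in follow-up, with AEs and SAEs collected at least by telephone or email. Only those who leave the study are affected.

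**Small in practice.** The trial stopped with 39 enrolled, late SAEs still reach the sponsor's safety group, and nothing in the documents points to a difference between arms. All of this stands, and it limits the size rather than removing the mismatch.

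**Conclusion.** The point holds in a limited form. For participants who leave the study less than 16 weeks after the last dose, the recording rule and the treatment-emergence definition do not match, and no visible text bridges them. If the outputs rest on the clinical database alone, treatment-emergent SAEs and deaths known to the sponsor are missing from them and entire-study rates are biased downwards. The denominator part does not depend on that inference, because SAP 2.7.1.1 counts time after all-causality SAE reporting has ended.

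The illustration of 3.3-3.5% rests on the planning drop-out of 10% and an assumed last visit 4 weeks after the last dose. The number of lost events cannot be derived, and no distortion of the comparison between arms is shown. How many of the 39 are affected is open: Protocol 9.4 treats participants as prematurely withdrawn after early termination, whereas SAP 1.1.2 says those on treatment were moved into follow-up. Those two passages must be reconciled.

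**What to change.** - **SAP 2.7.1 and 2.7.2, with a matching sentence in Protocol 10.1.3.** State that SAEs and deaths known to the sponsor with onset within 16 weeks of the last dose are transferred from the safety database at reconciliation before lock, and are included in the TESAE, AESI, death and registry outputs. Participants who withdrew consent are handled as in Protocol 9.2.
- **SAP 2.7.1.1.** End person-time at the earliest of the existing limits, death, or the end of SAE ascertainment. State which definition of treatment duration applies.
- **SAP 2.7.1.1 and 5.2.** Reconcile the Week 12 limit with the Week 12 cut-off date.
- **Protocol 9.4 and SAP 1.1.2.** Reconcile the status of participants at termination, and report how many left the study within 16 weeks of the last dose.

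The cost is a few sentences and a small reconciliation step. Reported SAE counts or rates may rise slightly. With recruitment closed, the SAP wording and the transfer before lock matter more than the change to 10.1.3.

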#### **10.1.4 Pregnancy reporting**

##### **Pregnancies**

If a female trial participant becomes pregnant, the study treatment should be stopped, and the pregnancy consent form should be presented to the trial participant. The participant must be given adequate time to read, review and sign the pregnancy consent form. This consent form is necessary to allow the investigator to collect and report information regarding the pregnancy. To ensure participant safety, each pregnancy occurring after signing the informed consent must be reported to Novartis within 24 hours of learning of its occurrence. The pregnancy should be followed up to determine outcome, including spontaneous or voluntary termination, details of the birth, and the presence or absence of any birth defects, congenital abnormalities, or maternal and/or newborn complications.

Pregnancy should be recorded and reported by the investigator to the Novartis Chief Medical Office and Patient Safety (CMO&PS). Pregnancy follow-up should be recorded on the same form and should include an assessment of the possible relationship to the study treatment for any pregnancy outcome. Any SAE experienced during pregnancy must be reported. After consent is provided, the pregnancy reporting will occur up to one year after the estimated date of delivery.

#### **10.1.5 Reporting of study treatment errors including misuse/abuse**

Medication errors are unintentional errors in the prescribing, dispensing, administration or monitoring of a medicine while under the control of a healthcare professional, participant or consumer (EMA definition).

Misuse refers to situations where the medicinal product is intentionally and inappropriately used not in accordance with the protocol.

Abuse corresponds to the persistent or sporadic, intentional excessive use of a medicinal product, which is accompanied by harmful physical or psychological effects.

Study treatment errors and uses outside of what is foreseen in the protocol will be recorded on the appropriate eCRF irrespective of whether or not associated with an AE/SAE and reported to Safety only if associated with an SAE. Misuse or abuse will be collected and reported in the safety database irrespective of it being associated with an AE/SAE within 24 hours of Investigator's awareness.

**Table 10-1 Guidance for capturing the study treatment errors including misuse/abuse**

Treatment error type	Document in Dosing eCRF (Yes/No)	Document in AE eCRF	Complete SAE form
Unintentional study treatment error	Yes	Only if associated with an AE	Only if associated with an SAE
Misuse/Abuse	Yes	Yes	Yes, even if not associated with a SAE

For more information on AE and SAE definition and reporting requirements, please see the respective sections.

## 10.2 Additional Safety Monitoring

### 10.2.1 Liver safety monitoring

To ensure participant safety and enhance reliability in determining the hepatotoxic potential of an investigational drug, a standardized process for identification, monitoring and evaluation of liver events has to be followed.

Please refer to [Table 16-3](#) in [Appendix 2](#) for complete definitions of liver laboratory triggers.

Once a participant is exposed to study treatment, every liver event defined in [Table 16-3](#) should be followed up by the investigator or designated personnel at the trial site, as summarized below. Additional details on actions required in case of liver events are outlined in [Table 16.4](#) and [Table 16.5](#). Repeat liver chemistry tests (i.e. ALT, AST, TBL, PT/INR, ALP and G-GT) to confirm elevation.

- These liver chemistry repeats will be performed using the central laboratory. If results will not be available from the central laboratory, then the repeats can also be performed at a local laboratory to monitor the safety of the participant. If a liver event is subsequently reported, any local liver chemistry tests previously conducted that are associated with this event should have results recorded on the appropriate eCRF.
- If the initial elevation is confirmed, close observation of the participant will be initiated, including consideration of treatment interruption if deemed appropriate.
- Discontinuation of the study treatment ([Section 9.1.1](#)), if appropriate
- Hospitalization of the participant if appropriate
- Causality assessment of the liver event

- Thorough follow-up of the liver event should include
  - These investigations can include based on investigator’s discretion: serology tests, imaging and pathology assessments, hepatologist’s consultancy; obtaining more detailed history of symptoms and prior or concurrent diseases, history of concomitant drug use, exclusion of underlying liver disease

All follow-up information and procedures performed must be recorded as appropriate in the eCRF.

### 10.2.2 Renal safety monitoring

The following base monitoring for renal laboratory values, as per the Novartis Drug-Induced Nephrotoxicity (DIN) Guidelines (Table 10-2 below) of abnormal renal laboratory values, will be carried out as part of the assessment schedule (Table 8-1) during the course of the study for those participants who have received study drug:

